#### Proportion of postoperative pain scores of NRS $\geq$ 4 during mobilization

Comparable to our co-primary outcome measure pain, the proportion of NRS measurements during mobilization ≥4 from POD 0 until 3 will be calculated by dividing the amount of NRS measurements ≥4 by the total amount of NRS measurements during mobilisation. Differences between randomization groups will be reported as percentages with 95% CIs and analysis will be done with a T-test or Mann-Whitney U test (Table 3).

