The sample size calculation resulted in 450 patients in total (150 for each randomization group) to demonstrate non-inferiority regarding proportion of NRS measurements ≥4 (power 99%, one-sided Type 1 error of 0.0135) as well as superiority regarding QoR (power 90%, two-sided Type 1-error of 0.027), taking into account an assumed 12.6% drop-out for conversions to thoracotomy (in the Netherlands, data from the Dutch Lung Cancer Audit from 2017) and controlling for the family-wise

error rate associated with the comparison of the two experimental groups (PVB and ICNB) with the same control group TEA (1).

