#### Analysis principles and general considerations

Continuous data will be reported as means with standard deviation (SD) or confidence intervals (CI), or medians with interquartile range (IQR) and will be compared between groups using the unpaired t-test or Mann-Whitney U, depending on the distribution of the data. Equality of variances for TEA and PVB, respectively ICNB, will be assessed with Levene's test. Categorical data will be presented as counts and percentages and data will be compared using Mantel-Haenszel Chi-squared test. In case of zero cell counts and when pooling of categories is not opportune, the Fisher's exact test will be used (7,8). For all secondary outcome measures, the CI and/or p-values will be provided to express the level of statistical significance per outcome without additional correction for multiplicity (also p<0.027). An overview of the planned statistical tests per outcome measure for group comparisons can be found in the Supplemental material (Appendix A).

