#### Analysis

For appointing non-inferiority, both the ITT and PP will be performed and both should attain to the predetermined non-inferiority margin (the one-sided 98.65% CI upper bound of the difference in proportions not exceeding 17.5%). For superiority (p<0.027), the ITT analysis will be considered as the primary analysis and the PP as a supportive analysis. For secondary outcome measures, solely the ITT analysis will be performed.

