#### Secondary outcomes

During hospital admission after surgery, all secondary outcomes will be measured from POD 0 until POD 3 and if applicable, until discharge from the hospital (e.g. duration of chest tube drainage). The follow-up outpatient clinic visit is at 2-4 weeks after surgery, according to local hospital protocols. Outcomes are collected up until 30 days after surgery, as described in the protocol. All secondary outcomes will be compared between TEA versus PVB and TEA versus ICNB in the ITT group and tested for statistical significance (p<0.027). The data will be presented as illustrated in Table 3.

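### For pain during mobilization, the 95% intervals planned for the group differences do not match the 0.027 level at which the SAP judges them

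*SAP*

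**What the plan says.** Three places in the SAP bear on this.

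- *Proportion of postoperative pain scores of NRS ≥ 4 during mobilization* sets the interval: "Differences between randomization groups will be reported as percentages with 95% CIs". For the test it says "analysis will be done with a T-test or Mann-Whitney U test (Table 3"). Appendix A names the same two tests.
- *Secondary outcomes* sets the threshold. All secondary outcomes are compared for TEA versus PVB and TEA versus ICNB and "tested for statistical significance (p<0.027").
- *Analysis principles and general considerations* gives the interval its role. For secondary outcomes, "the CI and/or p-values will be provided to express the level of statistical significance per outcome without additional correction for multiplicity (also p<0.027"). No confidence level is stated there.

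For co-primary pain the SAP does match interval to error rate. The *Summary of the study protocol* gives "power 99%, one-sided Type 1 error of 0.0135", and *Analysis* uses "the one-sided 98.65% CI upper bound of the difference in proportions not exceeding 17.5"%. For superiority on quality of recovery the level is stated as "power 90%, two-sided Type 1-error of 0.027".

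**The concern.** A confidence interval and a test agree only if they use the same error rate. A two-sided 95% interval excludes zero exactly when the matching test gives p<0.05. Here the threshold is 0.027, so a band of results would show an interval clear of zero beside a p-value that the plan counts as non-significant.

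Reporting 95% intervals next to a stricter test level is common and harmless when the intervals are labelled as estimation only. This SAP does not label them so. Its general rule says the interval may itself express significance at 0.027. At stake is a consistent reading of one secondary outcome for two comparisons. The inconsistency always runs towards claiming more than the plan allows.

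**Working it through.** **Inputs from the SAP**

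- Two-sided level 0.027, one-sided level 0.0135, 150 patients per arm, 12.6% drop-out (*Summary of the study protocol*).
- One-sided 98.65% bound for co-primary pain (*Analysis*).
- Two-sided 95% interval for the mobilization differences (its own section).
- Pilot SDs for pain at rest, 19.57 and 23.33 percentage points (*Summary of the study protocol*). These serve only to put the example on a scale.

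**1. The plan's own levels reproduce.** 2 × 0.0135 = 0.027, and 1 − 0.027/2 = 0.9865. A Dunnett-type correction for two comparisons with one control (correlation 0.5, family-wise 0.05, normal approximation) has critical value 2.212. This gives 0.02696 two-sided and 0.01348 one-sided, which round to the SAP's figures.

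**2. The matching interval.** 1 − 0.027 = 0.973, so 97.3% two-sided. The multipliers are z(0.9865) = 2.2115 and z(0.975) = 1.9600. Their ratio is 2.2115 / 1.9600 = 1.128, so the matching interval is 12.8% wider.

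**3. How often interval and test disagree, per comparison.** They disagree when the absolute test statistic lies between 1.960 and 2.212.

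- No true effect: 0.05 − 0.027 = 0.023, or 2.3%.
- True effect of m standard errors: Φ(2.2115 − m) − Φ(1.9600 − m). This is largest at m = 2.09, where it is 0.100. So 10% is a ceiling, not a typical rate.

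**4. Direction.** A 97.3% interval from the same t-test contains the 95% interval. So the 95% interval can exclude zero while p is 0.027 or more. It cannot include zero while p is below 0.027.

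**5. Example.** The SAP gives no SD for mobilization pain, so I assume the rest-pain pilot SDs.

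- Pooled SD = √((19.57² + 23.33²)/2) = 21.53.
- Evaluable per arm = 150 × (1 − 0.126) = 131.1, taken as 131.
- Standard error = 21.53 × √(2/131) = 2.66 points.
- The t multipliers on 260 degrees of freedom are 1.969 and 2.224. The band of disagreement is 1.969 × 2.66 = 5.2 to 2.224 × 2.66 = 5.9 points.
- At t = 2.10 the difference is 5.59 points with p = 0.037. The 95% interval is 0.35 to 10.83 and excludes zero. The 97.3% interval is −0.33 to 11.50 and includes it, in agreement with the test.

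The band in points moves with the SD and the sample size. The band in p, 0.027 to 0.05, does not.

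**The case against.** The strongest reply is that the decision rule is clear. *Secondary outcomes* tests at p<0.027, and the Table 3 shell has a row for this outcome with a p-value for each comparison. A reader of Table 3 will see the p-value. That stands, and it keeps the point small. It does not remove it, because the interval and the p-value can still point different ways, and the SAP does not say which prevails.

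Three stronger readings are tempting, and the document does not support them.

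- *That readers will see only the interval.* The wording in *Analysis principles and general considerations* would permit this in general, but Table 3 provides p-values for this outcome.
- *That the 95% intervals undo the trial's multiplicity correction.* For one outcome, reading significance from 95% intervals over both comparisons would give a family-wise error of about 9.1% instead of 5.0%. But the SAP sets out its family-wise control in the sample size for the co-primary outcomes. It reuses 0.027 for secondary outcomes without further correction, so there is no error control across the set of secondary outcomes to lose.
- *That all intervals in the plan are at the wrong level.* The explicit 95% for a between-group difference tested at 0.027 appears in the mobilization section only. The general section states no level. The 95% intervals under *Co-primary outcomes*, Pain, are for arm means and conflict with nothing.

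It can also be said that changing to 97.3% is not a complete cure, and this is right. If the Mann-Whitney U test is used, the interval of a difference in means is not derived from that test, and the two can disagree at any confidence level. The fix has to cover that case.

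**Conclusion.** The inconsistency is real and of low severity. For one secondary outcome, the stated 95% level does not match the 0.027 level that the SAP lets the interval express, whereas the co-primary pain bound does match its error rate. The sizes in steps 2 and 3 rest on the normal approximation and on interval and p-value coming from the same t-test. The example in points also rests on an assumed SD. The non-inferiority rule for pain and the superiority rule for quality of recovery are untouched.

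**What to change.** - In *Proportion of postoperative pain scores of NRS ≥ 4 during mobilization*, replace 95% with 97.3% two-sided for the between-group differences.
- In *Analysis principles and general considerations*, state that 97.3% is the level wherever the interval of a difference is given to express significance at 0.027.
- Add that, if the Mann-Whitney U test is used, significance rests on its p-value alone and the interval of the mean difference is descriptive.
- Leave the 95% intervals for arm means as they are.

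The cost is one number, two short sentences and a software setting, with intervals 12.8% wider. No new data are needed, and the sample size does not change.

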#### QoR-15

The QoR-15 score ranges from 0-150 and will be expressed as a discrete outcome. Repeated measurements of QoR measured by the QoR-15 questionnaire taken at baseline (preoperative), from POD 0 until POD 3 and at follow-up will be analysed by a linear mixed model to depict the trend over time between the different analgesic techniques (Figure 3b).

#### Cumulative use of opioids and analgesics

Additional analgesics (paracetamol and non-steroidal anti-inflammatory drugs) and opioids are recorded per day, from POD 0 until 3. When possible, opioids will be converted to oral milligrams of morphine equivalents (MMEs) using the conversion table (12); if not possible (e.g. sufentanyl), opioids will be reported as a separate row (see Table 3). This outcome will be described as a numerical continuous outcome in mg. Comparative analysis will be done with T-test or Mann-Whitney U test.

#### Postoperative complications

Postoperative complications are registered until 30 days after surgery and categorized according to the Clavien-Dindo (CD) classification (13). They will be pooled and analysed as minor complications (CD 1 and 2), major complications (CD 3 and 4) and mortality (CD 5). Comparisons will be done with Mantel-Haenszel chi-squared test or Fisher's exact test (Table 3).

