#### **Procedure ICNB**

```
Number of time executed

Executed at the end of the operation — no. (%)

Executed by the lung surgeon — no. (%)

Local analgesic given

Ropivacaine — no. (%)

Concentration ropivacaine (mg/mL)

Bupivacaine — no. (%)

Concentration bupivacaine (mg/mL)

Levobupivacaine — no. (%)

Concentration levobupivacaine (mg/mL)

Total volume given (mL)

From thoracic level 2 to 10 — no. (%)
```

Table 3: Secondary outcome measures

Outcome	Thoracic Epidural Analgesia (N=)	Paravertebral block (N=)	p-value 	Intercostal Nerve Block (N=)	p-value 
Percentage of NRS≥4 during mobilizing POD 0-3	()	(12)		(11)	
Percentage of NRS≥4 at rest POD 0-3					
Analgesics and opioids at POD 0					
Paracetamol (mg)					
NSAID's (mg)					
Opioids (MME)					
Optional: opioids when MME not applicable					
Analgesics and opioids at POD 1					
Paracetamol (mg)					
NSAID's (mg)					
Opioids (MME)					
Optional: opioids when MME not					
applicable					
Analgesics and opioids at POD 2					
Paracetamol (mg)					
NSAID's (mg)					
Opioids (MME)					
Optional: when MME not applicable					
Analgesics and opioids at POD 3					
Paracetamol (mg)					
NSAID's (mg)					
Opioids (MME)					
Optional: when MME not applicable					
Postoperative complications — no. (%)					
CD 1 and 2					
CD 3 and 4					
CD 5 (mortality)					
Hospitalisation (days)					
Time to removal of chest tube (days)					
Presence of urinary catheter (days)					
Plus-minus values are means ±SD. NRS denotes numerical		denotes postoperative of		tes milligrams of	

morfine equivalent; NSAIDs denotes non-steroidal anti-inflammatory drugs.CD denotes Clavien Dindo; p-value for the comparison between TEA and IVB; p-value for the comparison between TEA and ICNB

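### The major-complications row stops at Clavien-Dindo grade 4, so a severe complication that proves fatal can drop out of it; count grades 3 to 5 there and keep the mortality row and its test

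*SAP*

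**What the plan says.** Under Postoperative complications, the SAP registers events to 30 days, grades them by Clavien-Dindo (CD), and has them "pooled and analysed as minor complications (CD 1 and 2), major complications (CD 3 and 4) and mortality (CD 5". The test follows directly: "Comparisons will be done with Mantel-Haenszel chi-squared test or Fisher's exact test (Table 3".

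Table 3 carries the same split under one heading. Its rows are CD 1 and 2, CD 3 and 4, and "CD 5 (mortality", with p-value columns for each experimental arm against thoracic epidural analgesia (TEA). Appendix A has a single line for postoperative complications and adds no other comparison. No row or test for CD 3 and above, or for any complication, appears.

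The general analysis section gives Fisher's exact test a condition: "In case of zero cell counts and when pooling of categories is not opportune". It does not say which categories would be pooled. Secondary outcomes are judged "without additional correction for multiplicity (also p<0.027".

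**The concern.** In this SAP, CD 5 is death. A patient who has a severe complication and survives is CD 3 or 4 and counts as major. A patient whose equally severe complication is fatal becomes CD 5. Under highest-grade counting that patient is a non-event in the major row, so the row counts severe complications only among those who survive them. It falls as lethality rises.

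The Abstract lists complications among the outcomes to be tested for superiority, and the Background expects the alternatives to reduce morbidity. A favourable major-complications row would be read as support for that expectation. It should not become more favourable because more patients died.

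**Working it through.** **Inputs.**
- Randomised: "450 patients in total (150 for each randomization group".
- Assumed drop-out: 12.6% (Summary of the study protocol). Evaluable per arm: 150 × (1 − 0.126) = 131.1, taken as 131.
- Threshold: 0.027, read as two-sided as for quality of recovery (QoR), "superiority regarding QoR (power 90%, two-sided Type 1-error of 0.027".
- Event rates: none are given for complications or deaths, so every rate below is an assumption. There is likewise no planned power for this outcome to reproduce.

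**Step 1: direction of the displacement.** With highest-grade counting, rate(CD 3-4) = rate(CD 3-5) − rate(CD 5). Assume CD 3-5 is 10% in both arms.

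| Deaths, arm A vs arm B | CD 3-4, A vs B | Expected CD 3-4 patients of 131 | CD 3-5, A vs B |
|---|---|---|---|
| 1% vs 1% | 9% vs 9% | 11.8 vs 11.8 | 10% vs 10% |
| 1% vs 2% | 9% vs 8% | 11.8 vs 10.5 | 10% vs 10% |
| 1% vs 3% | 9% vs 7% | 11.8 vs 9.2 | 10% vs 10% |

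The arm with more deaths gains exactly its excess mortality as an apparent reduction in major complications. The direction follows from the definition. Only the size depends on the assumed rates.

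**Step 2: what the mortality row can show.** Fisher's exact test, two-sided, 131 per arm:
- 3 vs 0 deaths: p = 0.247
- 6 vs 0: p = 0.0295
- 7 vs 0: p = 0.0144, the first below 0.027 when the other arm has no deaths

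With 150 per arm the first significant split is again 7 vs 0 (p = 0.0145). For true mortality of 1% vs 3%, exact Fisher power is 3.4%; an uncorrected Mantel-Haenszel test gives about 11 to 12% by simulation.

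**Step 3: would the CD 3-5 row detect excess deaths better?** Take 13 CD 3-4 patients in each arm and add the deaths to one arm (131 per arm, Fisher p):

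| Deaths | Mortality row | CD 3-5 row |
|---|---|---|
| 3 vs 0 | 0.25 | 0.69 (16 vs 13) |
| 6 vs 0 | 0.029 | 0.35 (19 vs 13) |
| 7 vs 0 | 0.014 | 0.26 (20 vs 13) |

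It would not. When only deaths differ, the mortality test is the more sensitive one and has to stay.

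**Step 4: what the CD 3-5 row adds.** Simulated Mantel-Haenszel power at 0.027, 131 per arm, assumed rates:

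| CD 3-4 | Deaths | Power on CD 3-4 | Power on CD 5 | Power on CD 3-5 |
|---|---|---|---|---|
| 9% vs 15% | 1% vs 3% | 24% | 12% | 36% |
| 9% vs 17% | 1% vs 3% | 39% | 11% | 52% |

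There is a gain when severe non-fatal events and deaths move together, but power remains modest.

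**The case against.** The strongest reply is that two links in the argument are not in the text.

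First, the SAP does not say that the three rows are tested separately. Appendix A gives one line and one choice of test. The same Mantel-Haenszel test is planned for the five-level satisfaction scale and the four-level mobility scale, so it may be meant as one test across ordered classes, with death as the worst. The general section also contemplates pooling when a cell is zero, and 3 vs 0 deaths is such a case. This stands as an ambiguity. It does not remove the point, because neither an ordered test nor a pooling rule is fixed, and the three rows under p-value columns read more naturally as separate comparisons.

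Second, the SAP does not say whether patients or complications are counted. If complications are counted, other CD 3-4 events in a patient who dies remain in the major class and the displacement shrinks. This also stands, which is why the point is conditional.

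It is also fair to say that deaths are shown in the adjacent row of the same table, so nothing is hidden.

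Two stronger readings are tempting. A reader might infer that the plan has no usable way to register excess deaths. The document does not support that: a mortality comparison is planned and, although weak, it reacts sooner to excess deaths than the CD 3-5 row. A reader might also infer that mortality should therefore become purely descriptive. Step 3 argues against it, since that would drop the more sensitive of the two tests.

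**Conclusion.** The point holds as a minor improvement to a secondary outcome. The major class as written excludes fatal complications and no CD 3-and-above comparison exists. Under highest-grade counting and row-by-row testing, the major row is biased towards the arm with more deaths by the difference in mortality: 2 percentage points in the 1% vs 3% illustration.

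This rests on two natural but unstated readings (highest grade per patient, separate rows) and on assumed event rates. No changed conclusion has been shown, and the co-primary results for pain and QoR are not affected. Redefining the class corrects the direction of counting; it does not make the comparison well powered.

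**What to change.** In Postoperative complications and in Table 3, define major complications as patients with any CD grade 3 to 5, each patient counted once by highest grade. Keep the mortality (CD 5) row and its planned test. Stating the counting unit in the same sentence also settles whether patients or events are counted.

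The cost is one sentence and one redefined table row, using data already collected. The downside is that the major class then overlaps the mortality row; a table footnote can say that deaths appear in both.

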#### Length of Hospitalization

Days of hospitalization will refer to the LOS after the anatomical lung resection, reported in whole nights as outcome measure. Differences between groups will be analysed with a Mann-Whitney U test (Table 3).

#### Patient satisfaction

Patient satisfaction is scored from POD 0 until 3 in a patient diary using a 5-point Likert scale (extremely dissatisfied, dissatisfied, neutral, satisfied, extremely satisfied). This categorical outcome will be analysed as with Mantel-Haenszel chi-squared test or Fisher's exact test (Figure 4a).

Presence of chest tube

The presence of the postoperative chest tube will be registered in whole nights during hospital admission as outcome measure with differences between the groups analysed with T-test or Mann-Whitney U-test (Table 3).

#### Presence of urinary catheter

The presence of a postoperative urinary catheter will be registered as whole nights in which the urinary catheter was present during hospital admission as outcome measure with group differences analysed with T-test or Mann-Whitney U-test (Table 3).

#### Degree of mobility

Degree of mobility was recorded in the patient diary using a 4-point Likert scale (only in bed, from bed to chair, from bed to the toilet, outside of the patient room). This categorical outcome will be analysed with Mantel-Haenszel chi-squared test or Fisher's exact test (Figure 4b).

#### Cost-effectiveness of analgesic techniques

The cost-effectiveness analysis will be conducted and published separately and is not included in this statistical analysis plan.

#### Patient replacement and missing data

In the sample size calculation, we have considered 12.6% extra inclusions due to drop-outs after conversions to thoracotomy (late exclusion). Since this percentage is appropriately represented by data from the Dutch Clinical Audit database from 2017, we do not expect further patient

replacement. Clinical data management is performed by independent professional data managers from the Dutch Comprehensive Cancer Centre. Once inclusions are complete, careful inspection of the data will take place. The mechanism causing data to be missing, whether it is (completely) at random or not at random, will guide the study group to apply analytical methods to amend missing data.

The incidence of missing data is partially limited by study design where minimum numbers of measurements suffice to generate an outcome value. For our non-inferiority research question regarding pain, complete cases include patients with at least 3 NRS measurements during POD 0 until 2 or a LOS  $\leq$  2 days, to allow detection of curvilinear pain patterns over time for reliable imputation. The cut-off for LOS  $\leq$  2 days is established due to the expectation that patients who have been discharged from the hospital have a NRS score  $\leq$  4 (standard of care). For our superiority question regarding QoR, complete cases include patients with at least one QoR-score during POD 0 until 2.

In case of remaining patients with lacking outcome data below 5% of the study size (14), the baseline Table 1 will be reproduced for patients intended to be included in the analysis as complete cases and added to the supplementary material (15). Imbalances in covariate distributions across groups derived from observed SMDs in this table, will be assessed from a clinical perspective for potential bias in prognosis and adjusted for in a primary analysis based on complete cases.

In case of remaining patients with lacking outcome data at or above 5% of the study size, the same procedure will be followed including a reproduced baseline table. In addition, missing data patterns will be studied to assess the likelihood of data being missing (completely) at random. If data are likely to be missing completely at random, multiple imputation (e.g. K-nearest neighbour imputation; multiple imputation by chained equation) and inverse probability weighting will be applied with presumably prognostic co-variates to substantiate the findings of the primary analysis. If data are likely to be missing at random, exploratory subgroup analyses will be run to restrict the target population for implementation of study results to the subgroups of patients closest to the observed

effect estimate in the complete case analysis. Restriction on the generalizability of study results will be fully reported in the supplementary material and discussed in the manuscript.

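### The SAP says missingness not at random will guide the method but gives no route for it, so nothing planned tests how far unseen scores could shift the two co-primary conclusions.

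*SAP*

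**What the plan says.** All of this stands in the SAP under Patient replacement and missing data, unless another section is named.

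- The mechanism of missingness, "whether it is (completely) at random or not at random, will guide the study group to apply analytical methods to amend missing data".
- For pain, a patient is a complete case with at least 3 NRS readings over postoperative days (POD) 0 to 2, or with a length of stay (LOS) of at most 2 days. The LOS rule rests on "the expectation that patients who have been discharged from the hospital have a NRS score" of at most 4. For QoR, one score during POD 0 to 2 is enough.
- Below 5% of the study size lacking outcome data, the baseline table is reproduced for the complete cases, and relevant imbalances are "adjusted for in a primary analysis based on complete cases".
- The rule for higher rates opens with "In case of remaining patients with lacking outcome data at or above 5% of the study size". Those steps are then repeated and, beyond them, "missing data patterns will be studied to assess the likelihood of data being missing (completely) at random".
- Two branches follow. The first reads "If data are likely to be missing completely at random, multiple imputation" and adds inverse probability weighting, to support the primary result. The second reads "If data are likely to be missing at random, exploratory subgroup analyses will be run to restrict the target population".
- Under Analysis, non-inferiority needs the intention-to-treat (ITT) and per-protocol (PP) results to agree: "both should attain to the predetermined non-inferiority margin". QoR superiority is judged in ITT.

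**The concern.** The section names three mechanisms as determinants of the method and supplies methods for two. If the study group judges the data MNAR, the plan leaves it with the adjusted complete-case result. Below the 5% threshold that holds under any mechanism.

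The judgement itself cannot be made from the data. MAR and MNAR differ in how missingness depends on values nobody has seen, so no study of observed patterns can rule MNAR out. Any method chosen at that stage would be chosen after inspecting the data of a trial that could not be blinded (Summary of the study protocol).

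Both co-primary outcomes are patient-reported. If missingness depends on the unseen score, complete-case estimates are biased. In a non-inferiority comparison, losing high-pain patients from an intervention arm would favour the claim. Agreement between ITT and PP is no safeguard, because both can rest on the same complete cases.

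**Working it through.** **The routes side by side**

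| Situation | What the SAP provides |
|---|---|
| Below 5% lacking outcome data, any mechanism | Reproduced baseline table, adjusted complete-case analysis |
| 5% or more, judged MCAR | The same, plus multiple imputation and inverse probability weighting |
| 5% or more, judged MAR | The same, plus exploratory subgroup analyses to narrow the target population |
| Judged MNAR | No step |

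No other section fills the last row. Additional analyses offers regression for baseline imbalance and exploration by centre. The mixed models assume MAR and serve secondary outcomes. Appendix B, item 27e, refers to pages 11-15 for sensitivity analyses, but the outcome sections describe none for missing data.

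**Inputs.** From the Summary of the study protocol: pilot proportions 17.57% (SD 19.57) for thoracic epidural analgesia (TEA) and 21.21% (SD 23.33) for continuous locoregional analgesia, a difference of 3.64; margin 17.5; one-sided alpha 0.0135 (z = 2.2115); 150 per arm with 12.6% drop-out. From Interim and final analysis: 4 of 75 TEA patients had missing data, 5.3%. Assumed: missing fractions of 5% and 10%, observed differences d of 8 and 10, and missing TEA patients like the observed ones.

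**The plan's own figure.** 150 × (1 − 0.126) = 131 evaluable per arm. SE = √(19.57² + 23.33²)/√131 = 30.45/11.45 = 2.66. Power = Φ((17.5 − 3.64)/2.66 − 2.2115) = 99.9%, consistent with the stated 99%.

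**Tipping point for pain.** With a fraction m missing, the upper limit is UL = d + 2.2115 × 30.45/√(131(1 − m)). The shift among missing intervention patients that moves UL to the margin is (17.5 − UL)/m. The implied share of scores ≥4 in those patients is 17.57 + d + shift. The SE is held at its complete-case value.

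| m | d | UL | Shift needed (points) | Implied share ≥4 in missing patients |
|---|---|---|---|---|
| 5% | 3.64 | 9.7 | 157 | impossible |
| 5% | 8 | 14.0 | 69 | 95% |
| 5% | 10 | 16.0 | 29 | 57% |
| 10% | 3.64 | 9.8 | 77 | 98% |
| 10% | 8 | 14.2 | 33 | 59% |
| 10% | 10 | 16.2 | 13 | 41% |

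**Concentration in one arm.** 5% of 450 is 22.5, so 22 missing patients stay below the threshold. If all 22 were in one intervention arm, m = 22/131 = 16.8% and SE = √(19.57²/131 + 23.33²/109) = 2.81. UL is then 9.9, 14.2 and 16.2 for d = 3.64, 8 and 10, and the shifts needed are 45, 20 and 8 points. No sensitivity analysis would be triggered.

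**QoR.** The SAP does not state the planned effect. From 131 per arm, 90% power and two-sided alpha 0.027, it is (2.2115 + 1.2816) × √(2/131) = 0.43 SD. The smallest significant difference is 2.2115 × √(2/131) = 0.273 SD, or 0.288 SD with 118 per arm. At 10% missing, significance is lost if missing intervention patients are worse by (0.432 − 0.288)/0.10 = 1.4 SD, or by (0.432 − 0.273)/0.10 = 1.6 SD.

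**Readings outside the 5% count.** A patient with 3 of 8 readings, none ≥4, counts as complete at 0%. If the five unseen readings were all ≥4, the true value would be 5/8 = 62.5%. Readings after discharge are likewise unseen in patients who count as complete through LOS ≤2 days.

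**The case against.** The strongest reply is about size. The only missing-data rate in the SAP is 5.3%, in one arm at interim. The completeness rule keeps whole-patient missingness low, and differences of 8 and 10 are 2.2 and 2.7 times the pilot's 3.64. At 5% missing and the pilot difference, no shift can overturn the pain claim. That stands, and it limits the point.

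Four stronger readings are tempting, and the document does not support them.

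- *The complete-case result stands bare.* It does not: relevant imbalances are adjusted for at any missing percentage, and Additional analyses adds regression. These steps do not test MNAR, however.
- *The SAP's expectation of low pain after discharge shows that its missing patients are MNAR.* Those patients count as complete cases. The expectation is an untested assumption about unseen readings, and says nothing about patients who lack an outcome.
- *The worst patients in the intervention arms will be the missing ones.* Nothing in the SAP says so. It is a plausible direction of bias, which a sensitivity analysis should examine.
- *QoR superiority is easily lost.* At 10% missing, a deficit of 0.5 to 1 SD removes 0.10 × 0.5/0.432 = 12% to 0.10 × 1/0.432 = 23% of the back-calculated effect, which does not overturn it.

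It can also be said that the study group may choose a method later. The choice would then follow sight of unblinded data and rest on a judgement that the data cannot settle.

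**Conclusion.** The gap is real: the SAP announces MNAR as a guide to the method and gives it no route, and nothing planned shows how far unobserved scores would have to differ to change either co-primary conclusion. A reader might infer that non-inferiority is likely to be false or fragile. The figures do not show that. Under the pilot SDs and difference, 131 per arm and about 5% missing spread evenly, the pain claim cannot be overturned by missing patients. The check becomes informative in three cases: missingness nearer 10% (13 to 33 points suffice at d = 10 and 8), concentration in one arm (8 to 20 points with 22 patients in one arm), or an observed difference close to the margin. QoR at 10% missing needs a deficit of about 1.4 to 1.6 SD, given a 0.43 SD effect that is derived here and not stated in the SAP. The change should be made because it is cheap and would show either robustness or fragility.

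**What to change.** Replace the mechanism-dependent choice with one pre-specified delta-adjusted (tipping-point) sensitivity analysis for both co-primary outcomes: pain in ITT and PP, QoR in ITT.

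- Base it on multiple imputation under MAR, by arm. The present text ties multiple imputation to MCAR and sends MAR to subgroup restriction, so those branches must be amended first.
- Worsen the imputed values for the paravertebral and intercostal arms in fixed steps, for example 10 points in the proportion of NRS ≥4 and 0.25 SD in QoR, with TEA unchanged.
- Apply the delta also to missing readings within partly observed patients and to post-discharge readings of patients with LOS ≤2 days. A delta confined to patients without an outcome would miss both.
- Report the step at which the one-sided 98.65% limit reaches 17.5 points, or the QoR p-value reaches 0.027.

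The cost is a revision of the missing-data section and a little extra programming, with no new data. The downside is that a claim may be shown to be fragile.
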